## Strong or Moderate CYP3A inducers

Strong (e.g., phenobarbital, phenytoin, rifampicin, rifabutin, rifapentine, carbamazepine, nevirapine, enzalutamide and St John's Wort) and moderate CYP3A inducers (eg. bosentan, efavirenz, modafinil) of CYP3A should not be taken with olaparib.

If the use of any strong or moderate CYP3A inducers are considered necessary for the patient's safety and welfare this could diminish the clinical efficacy of olaparib.

If a patient requires use of a strong or moderate CYP3A inducer or inhibitor then they must be monitored carefully for any change in efficacy of olaparib.

*P-gp inhibitors* 

It is possible that co-administration of P-gp inhibitors (eg amiodarone, azithromycin) may increase exposure to olaparib. Caution should therefore be observed.

## Effect of olaparib on other drugs

Based on limited *in vitro* data, olaparib may increase the exposure to substrates of CYP3A4, P-gp, OATP1B1, OCT1, OCT2, OAT3, MATE1 and MATE2K.

Based on limited *in vitro* data, olaparib may reduce the exposure to substrates of CYP3A4, CYP1A2, 2B6, 2C9, 2C19 and P-gp.

The efficacy of hormonal contraceptives may be reduced if co administered with olaparib. Caution should therefore be observed if substrates of these isoenzymes or transporter proteins are co-administered.

Examples of substrates include:

- CYP3A4 hormonal contraceptive, simvastatin, cisapride, cyclosporine, ergot alkaloids, fentanyl, pimozide, sirolimus, tacrolimus and quetiapine
- CYP1A2 duloxetine, melatonin
- CYP2B6 bupropion, efavirenz
- CYP2C9 warfarin
- CYP2C19 lansoprazole, omeprazole, S-mephenytoin
- P-gp simvastatin, pravastatin, digoxin, dabigatran, colchicine
- OATP1B1 bosentan, glibenclamide, repaglinide, statins and valsartan
- OCT1, MATE1, MATE2K metformin
- OCT2 serum creatinine
- OAT3 -furosemide, methotrexate

#### **Anticoagulant Therapy**

Patients who are taking warfarin may participate in this trial; however, it is recommended that international normalised ratio (INR) be monitored carefully at least once per week for the first month, then monthly if the INR is stable. Subcutaneous heparin and low molecular weight heparin are permitted.

#### Anti-emetics/Anti-diarrheals

If a patient develops nausea, vomiting and / or diarrhea, then these symptoms should be reported as AEs and appropriate treatment of the event given.

## Administration of other anti-cancer agents

Patients must not receive any other concurrent anti-cancer therapy, including investigational agents, while on study treatment.

## 5.5.1 Medications that may NOT be administered

No chemotherapy, immunotherapy, hormonal therapy or other novel agent is to be permitted while the patient is receiving study medication.

# 5.6 Treatment compliance

## 5.6.1 Accountability

At each study visit patients will be asked about missed or lost doses. Pill diaries will be completed by the patients while on study. Pill bottles and any unused medications will be returned by the patient at each study visit. If diary is not returned at the time of the visit, the patient will be required to send the pill diary to the research coordinator. The investigational drug service (IDS) will count returned pills; the pill diaries and pill counts will be reconciled by the study coordinator using drug accountability CRF. Treatment compliance will be defined as the number of tablets taken during the study divided by the expected number of tablets, multiplied by 100%. Tablets that are not returned will be considered to have been taken, unless otherwise reported by the patient as not having been taken. Unused pills will be destroyed on site by the IDS.

# 5.7 Discontinuation of investigational product

Patients may be discontinued from investigational product (IP) in the following situations: Patient decision. The patient is at any time free to discontinue treatment, without prejudice to further treatment

Adverse Event

Severe non-compliance with the study protocol

Bone marrow findings consistent with myelodysplastic syndrome (MDS)/acute myeloid leukemia (AML)

## 5.7.1 Procedures for discontinuation of a subject from investigational product

If patient is discontinued from olaparib for one month continuous duration due to toxicity or other conditions, the patient will proceed to prostatectomy as clinically indicated.

# 5.8 Withdrawal from study

Patients may withdraw from study at any time. Patients who are unable to receive more than 6 weeks of olaparib prior to prostatectomy will be replaced to reach total target enrollment.

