## 3. STUDY PLAN AND PROCEDURES

# 3.1 Overall study design and flow chart

# 3.2 Rationale for study design, doses and control groups

This is an open-label, single center pilot study designed to assess the pathological complete response rate following neoadjuvant therapy (olaparib) of patients with localized prostate cancer for whom radical prostatectomy is indicated. Eligible patients are those with localized prostate cancer who are referred for radical prostatectomy. Patients should be either 1) carriers of a pathogenic germline variant of a gene involved in the homologous recombination pathway of DNA repair or 2) have evidence by somatic sequencing of biallelic inactivation of a gene involved in the homologous recombination pathway of DNA repair. It is anticipated that the majority of patients will be germline carriers of a pathogenic variant of BRCA1, BRCA2 or ATM. As previously discussed these patients are at high risk of micrometastatic disease at diagnosis and are therefore appropriate for approaches designed to test therapies which might induce tumor apoptosis, using pCR as a reflection of apoptosis and potential for elimination of micrometastases.

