## Primary Variable(s)

The primary efficacy variable is the proportion of patients achieving a pathological complete response of localized prostate cancer. Pathologic complete response is defined as the absence of morphologically identifiable carcinoma in the prostatectomy specimen, as evaluated by the site pathologist using standard methods (see the Laboratory Manual for detailed instructions). The expected complete response rate at prostatectomy without intervention is 1% or less and is 4% to 9%, with standard androgen deprivation in a mixed population of low-to-intermediate risk disease.

Tissue may also be assessed using methodologies in addition to standard morphological analysis, however, this will not be used to downgrade a pathological complete response.

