## **5.4.6** Early Termination Visit (Early Cessation of Study Drug)

Patients will be advised in the written informed consent that they have the right to withdraw from the study at any time without prejudice. The Principal Investigator or the Sponsor may discontinue a patient from study in the event of an intercurrent illness, adverse event, other reasons concerning the health or well-being of the patient, or in the case of lack of cooperation, non-compliance, protocol violation, or other administrative reasons.

For patients who have started study drug and terminate the study prematurely, every effort should be made to ensure the collection of safety data by means of unscheduled visits, the frequency and timing of which will be determined by the Principal Investigator, and the follow-up visit. If the patient is withdrawn from the study because of an adverse event or a serious adverse event, the event(s) must be followed as per section 6.4.3.

Patients who discontinue the trial prematurely may be replaced at the discretion of the Investigator.

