## 11. STATISTICAL METHODS AND SAMPLE SIZE DETERMINATION

### 11.1 Description of analysis sets

#### 11.1.1 Efficacy Analysis Set

Patients who receive olaparib for the complete planned neoadjuvant cycle and proceed to prostatectomy with tissue available for analysis of pathologic endpoints will be the efficacy analysis set. Patients who do not complete the treatment regimen or do not proceed to prostatectomy may be replaced in order to reach the target accrual for efficacy after discussion with principal investigator and sponsor

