## 11.3 Methods of statistical analysis

Statistical analyses will be performed using all patients with evaluable data (e.g., pathologic staging among those who had a prostatectomy, and safety data among those who receive a dose of olaparib).

For efficacy analysis pathologic complete response is defined as the absence of morphologically identifiable carcinoma in the prostatectomy specimen, as evaluated by the site pathologist using standard methods. Formalin-fixed, paraffin-embedded slides will be evaluated by a central pathology review at completion of the study. Comparison of the actual pathologic complete response rate with the historial rate of 10%.

For safety analyses, all patients who received at least one dose of study drug and had at least one post-baseline safety assessment will be evaluated. Data will be descriptive, describing frequency of grade 1-5 adverse events. Data from all cycles of treatment will be combined in the presentation of safety data. AE will be listed individually by subject. The number of subjects experiencing each AE will be summarized by the Medical Dictionary for Regulatory Activities (MedDRA) system organ class, MedDRA preferred term and CTCAE grade. The number and percentage of subjects with adverse events in different categories (e.g. causally related, CTCAE grade ≥3 etc.) will be summarized. Any AE occurring before the first dose of investigational product (i.e. before study Day 1) will be included in the data listings but will not be included in the summary tables of adverse events. Any AE occurring within the defined 90 day follow-up period after discontinuation of olaparib will be included in the AE summaries. Hematology, clinical chemistry, vital signs, ECG data, demographic data, medical histories and concomitant medications will be listed individually by subject. For all laboratory variables, which are included in the current version of CTCAE, the CTCAE grade will be calculated. Summary statistics of mean, median, standard deviation, minimum, maximum and number of observations will be used. Details of any deaths will be listed for all subjects.

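### Three inconsistent replacement rules, none timed before the specimen is read, combine with two conflicting denominators to leave room for outcome-dependent replacement

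*Combined protocol and SAP*

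**What the plan says.** Three sections govern replacement.

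- Section 5.8: "Patients who are unable to receive more than 6 weeks of olaparib prior to prostatectomy will be replaced to reach total target enrollment". It is mandatory and depends on exposure.
- Section 5.4.6: "Patients who discontinue the trial prematurely may be replaced at the discretion of the Investigator". It is optional, the investigator decides, and no exposure threshold is given.
- Section 11.1.1: "Patients who do not complete the treatment regimen or do not proceed to prostatectomy may be replaced in order to reach the target accrual". It is optional, after discussion with the principal investigator and sponsor, and covers any incomplete course.

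Two sections govern the denominator. Section 11.1.1 defines the efficacy set as "Patients who receive olaparib for the complete planned neoadjuvant cycle and proceed to prostatectomy with tissue available for analysis of pathologic endpoints". Section 11.3 says "Statistical analyses will be performed using all patients with evaluable data (e.g., pathologic staging among those who had a prostatectomy", which takes in everyone staged at surgery.

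The setting matters too. Section 3.2 states: "This is an open-label, single center pilot study designed to assess the pathological complete response rate". Under its Primary Variable(s) heading, pCR is read "as evaluated by the site pathologist using standard methods"; section 11.3 adds central review only when the study is complete. Under section 5.7.1, after a month continuously off olaparib "the patient will proceed to prostatectomy as clinically indicated". No section says when a replacement decision must be taken.

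**The concern.** The three rules differ in trigger, force and decision-maker. Take a man who stops olaparib at week 8 and then has his prostatectomy. Section 5.8 does not require his replacement, because he had more than 6 weeks. Section 11.1.1 permits it. His pathology can already be known at the site when the choice is made.

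If that choice followed the result, early stoppers with residual tumour could leave the count while early stoppers with pCR stayed in it. In a 15-patient single-arm comparison with a fixed 10%, one patient is 1/15 = 6.7 percentage points. Selection of this kind would raise both the estimated pCR rate and the false-positive chance.

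**Working it through.** **Inputs from the plan (sections 11.2 and 11.3).** Null pCR rate 10%, alternative 40%, N = 15, stated power 80%, two-sided alpha 0.05 (upper tail 0.025).

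**Input not in the plan.** The early-stop fraction e, meaning men who stop early but still have surgery. I assume 5%, 10%, 20% and 30%.

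**Step 1: the plan's own figure.** Exact binomial, n = 15, p = 0.10: P(X ≥ 4) = 5.6% and P(X ≥ 5) = 1.3%, so the rule is 5 or more pCRs. Power at p = 0.40 is P(X ≥ 5) = 78.3%, close to the stated 80%. The arcsine formula gives n = 14.9, rounded up to 15. The stated design reproduces.

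**Step 2: the worst case.** Each man stops early with probability e, independently of pCR. Early stoppers without pCR are replaced and leave the denominator; those with pCR are kept. A man is counted with probability 1 − e(1 − p), so the expected observed rate is

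r = p / [1 − e(1 − p)].

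For example, with p = 0.10 and e = 0.20: 0.10 / (1 − 0.18) = 0.122.

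| e | r if true pCR is 10% | P(≥5 of 15) if true pCR is 10% | r if true pCR is 40% |
|---|---|---|---|
| 0 | 10.0% | 1.3% | 40.0% |
| 5% | 10.5% | 1.5% | 41.2% |
| 10% | 11.0% | 1.9% | 42.6% |
| 20% | 12.2% | 2.8% | 45.5% |
| 30% | 13.7% | 4.4% | 48.8% |

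The 2.5% upper tail is still respected at e = 15% (2.3%) and exceeded at e = 20%.

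**Step 3: each analysis set applied strictly.**

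- Section 11.1.1: every man with an incomplete course is outside the set, with or without pCR and whether or not he is replaced. If stopping is unrelated to response, the expected rate stays at 10%.
- Section 11.3: an early stopper who had surgery stays in the denominator, so replacement adds a man and removes none. I keep the Step 2 trigger, enrol until 15 men are counted, retain the replaced men, and set the exact cutoff for the final N. The expected rate is then 10.1% at e = 20% and 10.2% at e = 30%, and the null rejection chance is 1.5% and 1.4%.

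The Step 2 table therefore needs a mixture: removal as in 11.1.1 for men without pCR and retention as in 11.3 for men with it.

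**Step 4: why the mixture is open.** Both denominators are in force, and the complete neoadjuvant cycle is not defined. Sections 5.4.10 and 5.4.12 allow repeated interruptions of up to 4 weeks each, Table 4 allows dose reductions, and section 5.4.4 gives surgery a window of ±14 days. Which men count as incomplete is therefore a judgement as well.

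**The case against.** The rules can be read as layers. Section 5.8 sets a mandatory floor, and section 11.1.1 adds an optional category that involves the sponsor. Section 5.4.6 speaks of leaving the trial, which a man who stops drug and goes to surgery has not clearly done, although its heading refers to stopping study drug. This softens the conflict. It still leaves the week-8 man to discretion and says nothing on timing.

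A reader might infer that replacement will be decided on the pathology result. The documents do not say so: the opportunity is inferred from their silence on timing, from the open-label single-centre design, and from section 5.7.1.

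A reader might also infer that the bias persists whichever analysis set is used. Step 3 shows otherwise. What persists is the conflict between the rules and the missing timing.

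The size may be small. Section 1.2.3 describes olaparib reactions as seldom forcing discontinuation, and treatment lasts only 90 days. At 5% or 10% early stopping the tail stays below 2.5%. That stands, and is why the lower rates are shown.

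Replacement itself is not the fault. Replacing early stoppers regardless of pathology does not bias the rate if stopping is unrelated to pCR.

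**Conclusion.** The inconsistency among sections 5.4.6, 5.8 and 11.1.1 is plain in the text, and so is the absence of any timing requirement. The bias is conditional. It needs the decision to be taken after the result is known and the two denominators to be mixed according to that result. It also assumes that every early stopper without pCR is replaced, that every one with pCR is kept, and that stopping is unrelated to response.

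On those terms the effect ranges from slight at 5% early stopping to material at 20% or more, where the upper-tail error passes 2.5%. The documents give no early-stop rate, so no single figure in the range can be preferred. The point warrants correction because the plan tests a stated null in 15 men and the gap is cheap to close.

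**What to change.** 1. Reconcile the three sections into one non-discretionary replacement rule based on a fixed exposure or no-surgery criterion. The existing criterion in 5.8 can serve. Have 5.4.6 and 11.1.1 refer to it, and delete their discretionary wording.
2. Decide and log each replacement, with the date, before the prostatectomy specimen is read.
3. Use the same criterion to define the efficacy set in 11.1.1 and 11.3, so that a man who is not replaced is analysed. If only the replacement rule changed, men with more than 6 weeks but an incomplete course would be neither replaced nor in the efficacy set, which could then fall below 15.
4. Report every replaced man, with his pathology if he had surgery. For illustration, 5/15 = 33.3% becomes 5/16 = 31.3% or 5/17 = 29.4% if one or two replaced men without pCR are put back in the denominator.

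The cost is protocol wording and a dated log. The investigator loses some discretion, and short-exposure men may count as non-responders.

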## 6. COLLECTION OF STUDY VARIABLES

# 6.1 Recording of data

Data delineated in section 5.4 will be collected and will also be entered into a study specific Redcap database for collation of patient characteristics and adverse events. Patients will maintain pill diaries which will be returned at each study visit and reconciled by the research coordinator and IDS as previously described. Pathologic stage at prostatectomy will be as per the pathology report by site pathologist and kept in the study binders.

# 6.2 Efficacy

The primary endpoint is to determine the pathologic complete response induced by the administration of olaparib at approximately 90 days (12 weeks). The primary efficacy analysis will estimate the proportion of patients who achieve a pathological complete response after neoadjuvant therapy upon radical prostatectomy. Pathologic stage (and complete response) will be assessed by pathologists at the institution. The detailed procedures for assessment of pathologic endpoints is contained in the laboratory manual.

# 6.3 Safety

The Principal Investigator is responsible for ensuring that all staff involved in the study is familiar with the content of this section.

## **6.3.1** Definition of adverse events

An adverse event is the development of an undesirable medical condition or the deterioration of a pre-existing medical condition following or during exposure to a pharmaceutical product, whether or not considered causally related to the product. An undesirable medical condition can be symptoms (e.g., nausea, chest pain), signs (e.g., tachycardia, enlarged liver) or the abnormal results of an investigation (e.g., laboratory findings, electrocardiogram). In clinical studies, an AE can include an undesirable medical condition occurring at any time, including run-in or washout periods, even if no study treatment has been administered.

The term AE is used to include both serious and non-serious AEs.

## 6.3.2 Olaparib adverse events of special interest

Adverse events of special interest [AESI] are events of scientific and medical interest specific to the further understanding of olaparib's safety profile and require close monitoring and rapid communication by the investigators to AstraZeneca. An AESI may be serious or non-serious. Adverse Events of Special Interest for olaparib are the Important Potential Risks of MDS/AML, new primary malignancy (other than MDS/AML) and pneumonitis.

ANY event of MDS/AML, new primary malignancy, or pneumonitis should be reported to AstraZeneca Patient Safety whether it is considered a non-serious AE [eg non-melanoma skin cancer] or SAE, and regardless of investigator's assessment of causality or knowledge of the treatment arm.

A questionnaire will be sent to any investigator reporting an AESI, as an aid to provide further detailed information on the event. During the study there may be other events identified as AESIs that require the use of a questionnaire to help characterize the event and gain a better understanding regarding the relationship between the event and study treatment.

#### 6.3.3 Definitions of serious adverse event

A serious adverse event is an AE occurring during any study phase (i.e., screening, run-in, treatment, wash-out, follow-up), at any dose of the study drugs that fulfills one or more of the following criteria:

Results in death

Is immediately life-threatening

Requires in-patient hospitalization or prolongation of existing hospitalization

Results in persistent or significant disability or incapacity

Is a congenital abnormality or birth defect

Is an important medical event that may jeopardize the patient or may require medical intervention to prevent one of the outcomes listed above.

The causality of SAEs (their relationship to all study treatment/procedures) will be assessed by the investigator(s) and communicated to AstraZeneca.

## 6.3.4 Recording of adverse events

Adverse events will be assessed at study visits and if necessary, at unscheduled evaluations.

## Time period for collection of adverse events

Adverse events and SAE will be collected from the time of patient consent until 30 days after prostatectomy.

#### 6.3.4.1 Adverse events after the 30 day follow up period

For Pharmacovigilance purposes and characterization, any case of MDS/AML or new primary malignancy occurring after the 30 day follow up period should be reported to AstraZeneca Patient Safety whether it is considered a non-serious AE (e.g., non-melanoma skin cancer) or SAE, and regardless of investigator's assessment of causality or knowledge of the treatment arm. Investigators will be asked during the regular follow up for overall survival if the patient has developed MDS/AML or a new primary malignancy and prompted to report any such cases.

At any time after a patient has completed the study, if an Investigator learns of any SAE including sudden death of unknown cause, and he/she considers there is a reasonable possibility that the event is causally related to the investigational product, the investigator should notify AstraZeneca, Patient Safety.

If patients who are gaining clinical benefit are allowed to continue study treatment post data cut off and/or post study completion then all SAEs must continue to be collected and reported to Patient Safety within the usual timeframe.

Otherwise, after study treatment completion (i.e. after any scheduled post treatment follow-up period has ended) there is no obligation to actively report information on new AEs or SAEs occurring in former study patients. This includes new AEs/SAEs in patients still being followed up for survival but who have completed the post treatment follow up period (30 days).

